3 INVESTIGATIONAL PLAN

3.1 General Schema of Study Design

This observational cohort study will evaluate clinical outcomes of inpatient versus outpatient management of neutropenia following chemotherapy in children with AML or MDS by abstracting data from medical records.

3.2 Study Duration, Enrollment and Number of Sites

The study plans to include patients treated for AML or MDS anytime from January 1, 2012 or after.

3.3 Total Number of Study Sites/Total Number of Subjects Projected

3.3.1 Duration of Study Participation

No direct patient contact is necessary for this study; only medical record abstraction. The chart abstraction window for each participant will include the time period from the start of the first course of chemotherapy until the date of last patient contact or death.

3.3.2 Total Number of Study Sites/Total Number of Subjects Projected

Chart abstraction will be conducted at the following seventeen US investigative sites: Ann Arbor (*C.S. Mott Children's Hospital*), Atlanta (*Children's Healthcare of Atlanta*), Chicago (*Ann & Robert H Lurie Children's Hospital of Chicago*), Dallas (*Children's Medical Center of Dallas – University of Texas Southwestern Medical Center*), Detroit (*Children's Hospital of Michigan*), Houston (*Texas Children's Hospital*), Jackson (*Children's of Mississippi*), Little Rock (*Arkansas Children's Hospital*), New Orleans (*Ochsner Medical Center for Children*), Palo Alto (*Lucile Packard Children's Hospital Stanford*), Philadelphia (*Children's Hospital of Philadelphia*), Salt Lake City (*Primary Children's Medical Center*), San Diego (*Rady Children's Hospital*), Seattle (*Seattle Children's Hospital*), Denver (*Children's Hospital of Colorado*), Nemours/A.I. duPont Hospital for Children, and DFCI/Boston Children's Hospital (*Boston, MA*). These sites were chosen based on geographic location, their substantial AML/MDS patient volume, and the variation in primary strategy of neutropenia management (inpatient versus outpatient).

We expect to identify a total of approximately 600 newly diagnosed AML patients across the seventeen participating institutions over the study period of which approximately 540 are expected to meet early discharge eligibility criteria.

3.4 Study Population

The study population will include all AML and MDS patients who received or will receive chemotherapy starting January 1, 2012 at any of the seventeen participating pediatric institutions across the US. Patients discharged within 3 days after completion of that chemotherapy course will be categorized as 'early discharge' to outpatient management during neutropenia. Patients meeting eligibility criteria for 'early discharge' but remaining in the hospital more than 3 days after completion of that chemotherapy course will be categorized as inpatient management. Patients will be considered early discharge-eligible if there is no evidence of fever, infection or intensive care unit (ICU) level care within \pm 3 days of the last dose of chemotherapy.

3.4.1Aim 1 Inclusion Criteria

- 1) Males or females less than 19 years of age at initial AML/MDS diagnosis.
- 2) Receipt or planned receipt of standard intensive AML frontline chemotherapy any time from January 1, 2012 or after.

3.4.2Aim 1 Exclusion Criteria

- Patients being treated for relapsed AML
- Patients with Acute Promyelocytic Leukemia (APML)
- Patients undergoing stem cell transplant (SCT)
- Patients receiving reduced intensity frontline chemotherapy

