2.2 Secondary Objectives

2.2.1 Identify subpopulations based on distinct longitudinal patterns of LV ejection fraction (EF) and fractional shortening (SF) decrease and recovery and evaluate the impact of bacteremia on the longitudinal patterns of LVEF and LVSF. Compare relapse risk (RR) and OS in subgroups.

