5 STUDY EVALUATIONS AND MEASUREMENTS

5.1 Screening and Monitoring Evaluations and Measurements

5.1.1 Medical Record Review

The following variables will be abstracted from the medical chart:

Variable Date of birth Sex Patient race/ethnicity Date of AML/MDS diagnosis Age at AML/MDS diagnosis Vital status Date of death or date of last known follow-up Location of death (in hospital or at home) AML subtype AML risk classification and cytogenetics Hospital admission start/stop dates Chemotherapy course Chemotherapy regimen and start/stop dates Course start/stop dates Clinical trial enrollment and specific protocol Documentation of deviation from planned chemotherapy course Presence/type of central line MRD post courses and dates of MRD obtained Post course remission status Daily max. fever; how was temperature taken Infections during chemotherapy courses ICU care during chemotherapy courses ANC measurements post chemotherapy Dates of ANC measurements Dates and results of microbiological cultures/PCRs onset during post chemotherapy course follow-up Mucositis by course Systematic antimicrobial prophylaxis at each course Height, weight, and body surface area at start of chemotherapy course Nutritional status/supplemental support requirements on day of chemotherapy completion Ability to practice oral hygiene Insurance status at course start (private, self-pay, public, other) English spoken? Home address Availability of working telephone Automobile/taxi voucher requirements Date of relapse Site of relapse Date of transplant Type of transplant Echocardiographic evaluations (e.g., dates, resulting measurements, measurement mode) Blood pressure and heart rate at echocardiographic evaluations Dexrazoxane administration Malignant blast percentage

| Bone marrow malignant blast percent |
|---|
| Empiric/definitive anti-infective use |
| Preferred language |
| Treatment and positive blood cultures at outside hospital (y/n) |
| Down Syndrome diagnosis |
| CNS status at the end of each course |
| Outpatient encounters (e.g., clinic/day hospital, ED) |

Some information will be retained for all screened patients to document the reasons for ineligibility. Specifically, we will be retaining information on age, leukemia diagnosis, treatment course, and whether the patient received reduced intensity chemotherapy.

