6.4 Sample Size and Power

Assuming 100% capture of eligible patients (waivers of consent obtained from all participating sites), we expect to identify a total of 600 newly diagnosed AML/MDS patients across the seventeen participating centers. Assuming 90% of identified patients will be early discharge eligible, the anticipated study population will be 540 patients. Based on the rates for the individual participating sites, approximately 27% of the study population will be managed as outpatients (n=146) and the remaining will be managed as inpatients (n=394) during neutropenia. Assuming a baseline risk of bacteremia of 60%, the proposed size of the two study arms would provide greater than 80% power to detect a 13% difference in bacteremia rates among patients managed as outpatients versus those that remain hospitalized, with a significance level of 0.05. A 13% difference in bacteremia rates would also be a clinically significant difference. For time to next chemotherapy course, we used a two sample t-test in the power calculation to be conservative (i.e., statistical analysis using a generalized linear model with correct distribution will result in creased power over a t-test). Assuming each patient contributes one treatment course and an average time to next chemotherapy course of 29 days and a standard deviation (SD) of 10 (based on preliminary data), our study will have 85.0% power to detect a difference of 3 days between the two groups, with a significance level of 0.05.

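### Entry is tied to any frontline chemotherapy from 1 January 2012, not to the first course, so patients who began in 2011 qualify by having survived; the relapse and transplant exclusions also lack a time point

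*Combined protocol and SAP*

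**What the plan says.** **Calendar rule.** Inclusion criterion 2 in 3.4.1 requires "Receipt or planned receipt of standard intensive AML frontline chemotherapy any time from January 1, 2012 or after". Section 3.2 repeats it: "The study plans to include patients treated for AML or MDS anytime from January 1, 2012 or after". Neither limits the date of diagnosis or of the first course. Section 3.3.1 sets the abstraction window "from the start of the first course of chemotherapy until the date of last patient contact or death".

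**Description of the cohort.** In 6.4, "we expect to identify a total of 600 newly diagnosed AML/MDS patients". Sections 3.3.2 and 8.4 also speak of new diagnoses, and 8.4 ties this to the retrospective period.

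**Exclusions.** Section 3.4.2 lists "Patients being treated for relapsed AML" and "Patients undergoing stem cell transplant (SCT", with no date or course at which either is judged. The contents list, by contrast, says that the protocol has no exclusion criteria.

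**Later events.** The variable list in 5.1.1 includes "Date of relapse Site of relapse Date of transplant Type of transplant", and objective 2.2.1 ends "Compare relapse risk (RR) and OS in subgroups".

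**Identification.** Retrospective patients are found by registry review (4.1.1), when their later history is already on file. Prospective patients are found through weekly contact with the inpatient leukemia service (4.1.2).

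**The concern.** A cohort followed from the first course should be entered at the first course. Here the qualifying event can be a later course. Someone who started in autumn 2011 and died, or stopped treatment, before the new year never appears. Someone who started on the same day and reached a January course appears with the whole record.

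Two analyses are exposed:

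- **Relapse and overall survival.** If time runs from the first course, the 2011 follow-up is time in which these patients could not have died before entry, so early risk is understated.
- **Time to next course.** A 2011 course is observed only if the patient was still receiving frontline chemotherapy in 2012. Failures to reach the next course before that date are missing. Among those who started longest before it, slow progress through the courses makes inclusion more likely.

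The undated exclusions raise a separate risk. If some sites apply them to patients who at any time relapsed or had a transplant, a retrospective site could drop a child whom a prospective site would already have enrolled.

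**Working it through.** **1. The plan's own counts.** From 6.4: 600 × 0.90 = 540; 540 × 0.27 = 145.8 (146 outpatients); 540 × 0.73 = 394.2 (394 inpatients). With a two-sided 5% test (sidedness is not stated), power for 60% versus 73% is 80.8%, in line with the stated figure of more than 80%. For 3 days with SD 10 it is 87.2%, against a stated 85.0%. The finding does not rest on these figures; they are used only to cost the fix.

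**2. The texts side by side.**

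| Text | Does a 2011 starter with 2012 chemotherapy qualify? |
|---|---|
| 3.4.1 criterion 2; 3.2 | Yes, read literally |
| 3.3.1 | Record taken from the 2011 first course |
| 3.3.2, 6.4 (newly diagnosed) | Suggests not, but no date is given |
| 8.4 (newly diagnosed in the retrospective period) | No |

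These cannot all hold.

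**3. How many patients.**

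- From the plan: 600 patients. Mean time to next course is 29 days, counted from three days after completion (6.1, 6.4), so completion to next course is 29 + 3 = 32 days.
- Assumed, because the documents give neither: accrual over 5 to 9 years, and four courses of 40 days each (8 days of chemotherapy plus the 32 days).
- Criterion 2 needs chemotherapy in 2012, so recovery after the last course does not count. The qualifying span before 1 January 2012 is 3 × 40 + 8 = 128 days.
- Annual accrual: 600/9 = 66.7 to 600/5 = 120.
- Affected: 66.7 × 128/365 = 23.4, up to 120 × 128/365 = 42.1.
- Share: 23.4/600 = 3.9%, up to 42.1/600 = 7.0%.

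This takes accrual as steady and ignores death or withdrawal within the 128 days. It also includes patients whose first course was itself under way on the date. Counting only those with a later course starting in 2012 uses 120 days and gives 66.7 × 120/365 = 21.9 to 120 × 120/365 = 39.5.

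**4. If the exclusions were read as ever relapsed or ever transplanted.** Dropping patients who later relapse would lower the observed relapse risk. It would raise observed survival, because deaths after relapse are lost. For bacteremia, suppose a true risk ratio of 1.0, a 60% risk in both arms and 95% of non-bacteremic patients retained (retention figures assumed). If a fraction r of bacteremic patients is retained, the observed risk is 0.6r / (0.6r + 0.4 × 0.95).

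- r = 0.90: 0.54/0.92 = 0.587.
- r = 0.80: 0.48/0.86 = 0.558.
- Equal retention (0.90 in both arms): risk ratio 1.00.
- Inpatients 0.90, outpatients 0.80: 0.558/0.587 = 0.95.

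So with no true difference, a spurious one needs retention to depend on both arm and bacteremia.

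**The case against.** The best defence is that the authors plainly meant a newly diagnosed cohort. Sections 3.3.2, 6.4 and 8.4 say so, 3.4 speaks of chemotherapy starting on 1 January 2012, and 4.1.1 looks for patients from that date. This is good evidence of intent. It does not settle the matter: sites screen against the numbered criterion, 3.2 repeats it without a limit, and nothing bars 2011 courses from analysis. If only courses started from that date were analysed, the survivor problem in the course-level data would go.

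A reader might infer more from 3.4.2: that it removes everyone who later relapsed or had a transplant, or that retrospective sites may choose whom to keep. The documents do not support either reading.

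- Both exclusions are in the present tense, and 3.4 classifies patients by course.
- Collecting relapse and transplant dates, and comparing relapse and survival, makes sense only if such patients stay in.
- Section 3.4 includes all patients, 6.4 assumes full capture, and 4.1.3 standardises abstraction. No discretion is given.
- The step from 600 to 540 is not evidence of a conflict, since 600 may already be net of exclusions.
- The documents give neither the share who relapse or have a transplant nor the retrospective share, so no count of patients at risk of being dropped can be supported.

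It would also be too strong to say that the primary comparisons are biased. Relapse and survival are compared across subgroups by left ventricular function, not between early discharge and inpatient care. The effect on bacteremia is conditional, as shown in the working. The size and direction of any effect on the between-arm difference in time to next course cannot be worked out from the documents.

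**Conclusion.** The calendar rule is a real defect in stated text. Criterion 2 and section 3.2 let in patients already on treatment on 1 January 2012, 3.3.1 brings in their 2011 record, and three other sections describe a different cohort. On the assumptions given (5 to 9 years of accrual, four 40-day courses, 32 days between completion and the next course), about 23 to 42 of 600 patients, or 4% to 7%, are affected. The consequences are immortal time in relapse and overall survival if these are timed from the first course, and left truncation of the 2011 courses in the time-to-next-course data. At this share the distortion is probably modest, but it is avoidable.

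The missing time point in 3.4.2 is an ambiguity, not a demonstrated error, and nothing shows that any site has excluded patients wrongly. It still deserves a sentence, because staff at seventeen sites work from this text and misapplication would be hard to detect: the items that 5.1.1 retains on ineligible patients are age, leukemia diagnosis, treatment course and reduced-intensity chemotherapy. Relapse and transplant are not named.

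**What to change.** **Calendar rule.** Reword 3.4.1 and 3.2 to require that the first frontline course started on or after 1 January 2012. Alternatively, keep these patients, analyse only courses started from that date, and use delayed entry for relapse and survival. Align 3.3.2, 6.4 and 8.4 with the choice.

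Cost: under the first option these patients are lost; under the second, only their 2011 courses. If 600 already means new diagnoses, the planned numbers do not change. If it includes the 2011 starters, 540 × (1 − 23.4/600) = 519 and 540 × (1 − 42.1/600) = 502. With the 27/73 split kept, power for 60% versus 73% falls from 80.8% to between 79.2% and 77.8%, and for 3 days from 87.2% to between 85.9% and 84.7%.

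**Exclusions.** State in 3.4.2 that relapse and transplant status is judged at the start of each index course. State that patients with later relapse or transplant stay in for their preceding frontline courses and for relapse and survival. Add both to the recorded screening reasons in 5.1.1, and correct the contents list.

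Cost: rewording, plus a recheck of the retrospective sites' registries for anyone dropped on an ever-relapsed or ever-transplanted reading. The recheck has to go to the registries, because the screening record may not hold the reason.

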4 STUDY PROCEDURES

4.1 Aim 1

The only study procedure for this cohort is chart abstraction; thus, there will be no study visits or other patient contact encounters required from the participant.

4.1.1 Retrospective Patient Identification:

Local study investigators (pediatric oncologists and study coordinators) at each of the seventeen participating pediatric institutions will review their hospital AML or MDS registry to identify patients from January 1, 2012 through the date of IRB approval that meet enrollment criteria.

4.1.2 Prospective patient identification:

The prospective data abstraction timeline begins the date of IRB approval and lasts through the duration of the study. Study investigators at each institution will communicate on a weekly basis with their inpatient leukemia service to identify AML or MDS patients potentially eligible for study enrollment. Once identified, study personnel will review each patient for study eligibility criteria.

4.1.3 Data Abstraction

For all enrolled patients, chart abstraction will be performed by CHOP personnel or local site staff using standardized data abstraction processes. Trained CHOP study personnel will first abstract data for CHOP patients identified between January 1, 2012 and date of IRB approval. They will then travel to the other 16 sites to assist and educate local study personnel on the chart abstraction procedures for patients identified at those institutions. Alternatively, CHOP personnel can perform medical record abstraction remotely for sites who grant CHOP remote EMR access. All data will be abstracted directly into REDCapTM via standardized electronic case report forms developed by CHOP study personnel. Details on data to be abstracted from the medical record are included in sections 5.1.1 and 6.1 below.

4.2 Subject Completion/Withdrawal

This is an analysis of data that are documented in the course of providing clinical care to subjects. As there are no additional interventions necessary for the execution of this study and we do not foresee any adverse effects stemming from the research, a waiver of consent will be submitted to address the issue of subject withdrawal.

5 STUDY EVALUATIONS AND MEASUREMENTS

5.1 Screening and Monitoring Evaluations and Measurements

5.1.1 Medical Record Review

The following variables will be abstracted from the medical chart:

Variable Date of birth Sex Patient race/ethnicity Date of AML/MDS diagnosis Age at AML/MDS diagnosis Vital status Date of death or date of last known follow-up Location of death (in hospital or at home) AML subtype AML risk classification and cytogenetics Hospital admission start/stop dates Chemotherapy course Chemotherapy regimen and start/stop dates Course start/stop dates Clinical trial enrollment and specific protocol Documentation of deviation from planned chemotherapy course Presence/type of central line MRD post courses and dates of MRD obtained Post course remission status Daily max. fever; how was temperature taken Infections during chemotherapy courses ICU care during chemotherapy courses ANC measurements post chemotherapy Dates of ANC measurements Dates and results of microbiological cultures/PCRs onset during post chemotherapy course follow-up Mucositis by course Systematic antimicrobial prophylaxis at each course Height, weight, and body surface area at start of chemotherapy course Nutritional status/supplemental support requirements on day of chemotherapy completion Ability to practice oral hygiene Insurance status at course start (private, self-pay, public, other) English spoken? Home address Availability of working telephone Automobile/taxi voucher requirements Date of relapse Site of relapse Date of transplant Type of transplant Echocardiographic evaluations (e.g., dates, resulting measurements, measurement mode) Blood pressure and heart rate at echocardiographic evaluations Dexrazoxane administration Malignant blast percentage

| Bone marrow malignant blast percent |
|---|
| Empiric/definitive anti-infective use |
| Preferred language |
| Treatment and positive blood cultures at outside hospital (y/n) |
| Down Syndrome diagnosis |
| CNS status at the end of each course |
| Outpatient encounters (e.g., clinic/day hospital, ED) |

Some information will be retained for all screened patients to document the reasons for ineligibility. Specifically, we will be retaining information on age, leukemia diagnosis, treatment course, and whether the patient received reduced intensity chemotherapy.

6 STATISTICAL CONSIDERATIONS

6.1 Primary Endpoint

The primary outcomes will include the following two endpoints (ascertained from patient medical records):

1.) Occurrence of post-chemotherapy bacteremia

Identification of bacteremia will begin three days after completion of a chemotherapy course and will continue until recovery of neutrophil count (ANC > $200~\mu L$), or until the start of the next course (for a very small number of patients who begin the next course of chemotherapy prior to count recovery). Bacteremia will be defined as a single positive blood culture for a bacterial pathogen (including Viridans group Streptococci). If the bacterium is an organism considered as a common commensal organism by the National Healthcare Safety Network, two separate positive blood cultures will be required for classification as bacteremia.

2.) Time to the initiation of the next chemotherapy course

Time to next course of chemotherapy will be measured as the number of days from the three days after the completion chemotherapy in a given course until the first day of the next course.

6.2 Control of Bias and Confounding

This is an observational cohort study, so subjects are not assigned by a process of randomization and are therefore subject to bias. However, analyses of our data will control for potential confounding by various patient- and hospital- level factors. Additionally, there is a possibility of exposure misclassification given that patients who are discharged more than 3 days after chemotherapy completion but well before neutropenia recovery will still be included in the inpatient management group. To account for this imperfect specificity, sensitivity analyses will be performed utilizing a less strict threshold for discharge classification (e.g., 5- or 10 days post-chemotherapy).

